1.0 DEVICE DESCRIPTION

The Hydrus Microstent is a crescent-shaped implantable device pre-loaded onto a hand-held delivery system.

The Hydrus Microstent is composed of nitinol, a metal alloy of nickel (Ni) and titanium (Ti). Nitinol has been used extensively in a variety of implantable vascular and orthopedic devices for its proven properties of flexibility, strength and biocompatibility. As a shape memory alloy, nitinol has super elastic properties making it suitable as a support structure in Schlemm's canal. The Hydrus is approximately 8mm in overall length. The major and minor axes of the implant are 292 μ m and 185 μ m, respectively.

The implant is laser cut to a proprietary design with alternating "spines" for structural support and "windows" to provide outflow pathways for aqueous humor. After laser cutting, the shape of the implant is heat-set to a curvature that matches the curvature of Schlemm's canal and is electro-polished to create a smooth biocompatible surface. The length and curvature of the implant are designed to occupy approximately 90° or 3 clock hours of Schlemm's canal. The implant is designed to have adequate structural thickness to support the tissue of the canal while providing maximum open flow areas through the canal, with the proximal portion of the implant exiting the canal through the trabecular meshwork to allow inflow of aqueous humor from the anterior chamber.

The **Hydrus Delivery System** is a hand-held mechanical device that provides for manual delivery of the Hydrus Microstent through a stainless steel cannula into the target site in the eye. The delivery system was designed for usability to provide smooth tracking and controlled delivery of the microstent into Schlemm's canal. The hand piece is an ergonomic design for use in either the right or left hand, allowing for surgeon individual preference and hand position. To accommodate a wide range of hand positions, a rotatable sleeve at the distal end allows positioning and alignment of the cannula by the surgeon to direct the implant into Schlemm's canal. The tracking wheel on the delivery system serves as the control mechanism to advance the implant into the canal or retract the implant into the cannula.

To deliver the microstent into Schlemm's canal, the cannula of the delivery system is inserted through a clear corneal incision (approximately 1.5mm in length). The cannula tip is then advanced through the trabecular meshwork until it enters Schlemm's canal and the entry point into the meshwork is coincident with the end of the cannula bevel. The target tissue is visualized using a gonioscopic prism. After observing that the distal cannula tip is properly positioned through the trabecular meshwork into Schlemm's canal, the tracking wheel on the delivery system is used to advance and release the microstent.

The Hydrus Microstent is packaged in sterile-barrier packaging and provided "STERILE" by gamma irradiation.

2.0 SUMMARY OF NONCLINICAL STUDIES

2.1 Biocompatibility Testing

The selection of biocompatibility tests of the Hydrus Microstent was based on guidelines presented in EN ISO 10993-1 Biological evaluation of medical devices - Part 1: Evaluation and testing within a risk management process and ANSI Z80.27-2014- Aqueous Shunts for Glaucoma

Applications (Section 4.2) with specific requirements applicable to metallic or non-polymeric implants as described in ANSI Z80.27, Section 6.3.

The biocompatibility of the Hydrus Microstent and the Hydrus delivery system has been established through studies conducted by Wu-Xi AppTec, Inc. (St. Paul, MN) in accordance Good Laboratory Practices (GLP) and with EN ISO 10993-1 and parts 3, 5, 6, 10 and 11 for specific test requirements. For tests requiring extracts, coupons of nitinol were utilized rather than the Hydrus Microstent itself due to the very small mass and surface area of the Hydrus Microstent. The coupons were made of the same nitinol material and processed in a manner representative of production processes utilized to manufacture the implant, including laser cutting, electropolishing, cleaning and gamma irradiation.

The delivery system is classified as having limited (<24 hours) ocular tissue contact. To demonstrate biocompatibility, cytotoxicity, delayed hypersensitivity, and intracutaneous irritation testing were performed. All results were negative for toxic effects. For the Hydrus Microstent, tested for permanent (>30 days) ocular tissue contact, the following studies were performed: cytotoxicity, material mediated pyrogen, acute systemic toxicity, delayed hypersensitivity, intracutaneous irritation, mutagenicity/genotoxicity, subacute toxicity, subchronic toxicity and muscle implantation (13 weeks). Additionally, a 6-month ocular implantation study was conducted in rabbits. The results of testing on the Hydrus Microstent are summarized in Table 2 below. No biological toxicity was observed in any of the above test systems as identified in the test-specific ISO 10993 standards.

Additionally, chemical characterization of extractables and leachables materials was performed by Legend Technical Services with review and a toxicological risk assessment performed by a qualified expert. These studies demonstrated negligible risk to health due to materials extracted or leached from nitinol samples representative of the implant. A follow-on longer-term nickel elution study by WuXi AppTec using Hydrus Microstent as the test article confirmed the finding of negligible health risk from eluted nickel from the implant.

TABLE 2
RESULTS OF BIOCOMPATIBILITY TESTING ON HYDRUS MICROSTENT

| ISO 10993 | TEST | RESULT |
|-----------|--|---------------|
| Part 3 | Mutagenicity/Genotoxicity, Bacterial Reverse Mutation Study – saline and DMSO extracts | Non-mutagenic |
| Part 3 | In vitro Mouse Lymphoma Assay – 2 extracts | Non-genotoxic |
| Part 3 | In vivo Mouse Micronucleus Assay – 2 extracts | Non-genotoxic |
| Part 5 | Cytotoxicity Study using ISO Elution Method - MEM | Non-toxic |
| Part 5 | Cytotoxicity Study using ISO Agarose Overlay Method | Non-toxic |
| Part 6 | Muscle Implantation Study (13 weeks) | Non-irritant |

| | | |
|---------|--|--|
| Part 6 | Chronic Ocular Implantation Study in Rabbits (6 months) | Non-inflammatory Non-toxic |
| Part 10 | Delayed Hypersensitivity (Maximization) Study - saline and sesame oil extracts | Non-sensitizing |
| Part 10 | Intracutaneous Irritation Study - saline and sesame oil extracts | Non-irritant |
| Part 11 | Acute systemic toxicity - saline and sesame oil extracts | Non-toxic |
| Part 11 | Subacute toxicity (intraperitoneal) - sesame oil extract | Non-toxic |
| Part 11 | Subchronic toxicity (intravenous) - saline extract | Non-toxic |
| Part 11 | Material mediated pyrogen (rabbit) | Non-pyrogenic |
| Part 18 | Chemical Hexane Extraction and Saline Leach Study | Negligible risk from extracted/leached materials |
| Part 18 | Nickel Elution Study | Negligible risk from eluted nickel |

3.0 STUDY METHODS

3.1 Selection of Patients

Only subjects who meet the inclusion and exclusion criteria will be eligible for surgery in this study.

3.2 Screening Inclusion Criteria

Subjects must meet the following inclusion criteria to be eligible. Unless otherwise specified, all ocular criteria refer to the study eye only.

- Male and female patients at least 45 years of age
- A diagnosis of open-angle glaucoma (POAG, PXG, or PG), with optic nerve pathology described by one or more of the following:
 - Diffuse thinning, focal narrowing, or notching of the optic disc rim, especially at the inferior or superior poles with or without disc hemorrhage;
 - Localized abnormalities of the peripapillary retinal nerve fiber layer, especially at the inferior or superior poles; or
 - Optic disc neural rim asymmetry of the two eyes consistent with loss of neural tissue
- BCVA of 20/80 or better in the study eye
- Subject has refractory glaucoma, defined as:
 - Previously failed filtering or cilioablation procedure (i.e., includes incisional glaucoma surgery, cryotherapy, and cyclodiode therapy) and with uncontrolled IOP on medical therapy

or

- IOP is uncontrolled on maximum tolerable medical therapy (e.g., a minimum of four or more classes of topical glaucoma medications, or fewer if others are not tolerated or are not effective)
- Subject has been on current glaucoma medication regimen for at least 30 days
- A medicated IOP of ≥ 20 mmHg and ≤ 35 mmHg by Goldmann applanation tonometry
- Open anterior chamber angle anatomy (e.g., no peripheral anterior synechiae or iris processes) visualized by gonioscopy with a Shaffer angle grade of \geq III in all four quadrants
- Visual field examination using Humphrey-Zeiss 24-2 SITA Std., with mean deviation (MD) of -3 dB or worse (conducted within 60 days of Screening is acceptable)
- Visual field defects consistent with glaucomatous optic nerve damage, and with at least one of the following two findings:
 - A cluster of 3 or more points in an expected location of the visual field depressed below the 5% level, at least 1 of which is depressed below the 1% level on pattern deviation (PD) plot
 - Glaucoma hemi-field test “outside normal limits”
- The subject is able to understand the requirements of the study and provide written informed consent
- Subject is willing to follow study instructions, agrees to comply with all study procedures and attend all scheduled follow-up exams for 12 months postoperatively

3.3 Screening Exclusion Criteria

Excluded from the study will be individuals with the following characteristics. Unless specified otherwise, all ocular criteria refer to the study eye only.

- Secondary glaucoma other than pseudoexfoliative and pigmentary (e.g., neovascular, uveitic, traumatic, steroid induced, lens induced, or glaucoma associated with increased episcleral venous pressure)
- Diagnosis of acute angle closure, chronic angle closure, or congenital, malignant, or developmental glaucoma
- Central visual field depression within 5 degrees of fixation with sensitivity < 15 dB in both hemifields on the numerical/dB plot
- Pre-perimetric glaucoma
- Ocular hypertension
- Shallow or flat anterior chamber
- Presence of peripheral anterior synechiae or iris processes obscuring angle visualization
- Central corneal thickness greater than 620 or less than 480 microns
- History of complicated intraocular surgery (e.g., vitreous in anterior chamber, zonular dehiscence)
- History of failed Schlemm's canal procedure (including but not limited to Glaukos iStent, Ellex ABiC, SightSciences Trab360, or New World Medical Kahook Dual Blade)
- Epithelial or fibrous downgrowth

- Aphakia
- Currently implanted anterior chamber IOL
- Retinal laser within 90 days prior to screening
- A need for additional ocular surgery (e.g., cataract surgery) or retinal laser procedure within the 12-month postoperative period
- Proliferative diabetic retinopathy (PDR)
- History of retinal detachment repair with silicone oil or scleral buckling procedure
- Corneal dystrophy (e.g., Fuch's Dystrophy, defined as > 12 confluent endothelial guttae) or corneal opacity
- Previous corneal surgery, including lamellar or penetrating keratoplasty, LASIK or PRK
- Fellow eye best-corrected visual acuity (BCVA) worse than 20/200
- Inability to complete a reliable Humphrey-Zeiss 24-2 SITA Std visual field on the study eye (fixation losses, false positive, and false negative errors should not be greater than 33%)
- Fellow eye visual field mean deviation worse than -18.00 dB
- Exudative age-related macular degeneration (AMD)
- History of intraocular inflammation or infection within 90 days prior to screening
- Use of oral hypotensive medication (e.g., acetazolamide) for glaucoma treatment
- Uncontrolled systemic disease that in the opinion of the Investigator would put the subject's health at risk and/or prevent the subject from completing all study visits
- Unable to suspend or temporarily discontinue use of blood thinners (e.g., warfarin, heparin, aspirin, etc.) in accordance with surgeon's standard instructions
- Pregnant or nursing women; or women of child bearing age not using medically acceptable birth control
- Current participation or participation within the past 30 calendar days in another investigational drug or device clinical trial
- Known or suspected allergy to nickel

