5.2 Study Populations

The **Effectiveness Population** will consist of all the subjects who undergo the Hydrus implantation surgery and are not discontinued early from the study due to unrelated reasons such as death or relocation. The primary analyses on the primary and secondary effectiveness endpoints will be based on the **Effectiveness Population**. The reasons for discontinuation will be reported.

Intent to Treat. The ITT population will include all subjects undergoing Hydrus Microstent implantation surgery. For this study the ITT population is the safety population.

Per Protocol. The Per Protocol (PP) population will include all implanted subjects who meet the following criteria:

- Subject meets all protocol eligibility criteria.
- Subject completes the 12-month visit.
- Subject received secondary surgical intervention (SSI) for controlling IOP will be included and treated as non-responder
- Subjects without adverse events that lower IOP such as cyclodialysis cleft.
- Additional criteria, if any, will be established before the data review and database closure.

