5.3 Effectiveness Endpoints Analyses

5.3.1 Primary Effectiveness Endpoint

The primary effectiveness outcomes for this study is:

- Proportion of subjects with $\geq 20\%$ decrease in mean diurnal IOP at 12 months while maintaining the same or fewer number of medications as at baseline

The primary analyses of the primary endpoint will be based on the Effectiveness Population. The exact 95% confidence interval of the response rate will be calculated based on binomial distribution.

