6.8.1 Anticipated Adverse Events

Anticipated AEs associated with glaucoma surgical procedures that might reasonably be expected to occur in this study are listed below. These specific examples of anticipated AEs include, but are not limited to:

Intraoperative Adverse Events

- Choroidal hemorrhage or effusion
- Corneal abrasion
- Corneal edema
- Cyclodialysis cleft
- Hyphema obscuring the surgeon's view
- Inadvertent perforation of the sclera
- Iridodialysis
- Lens / capsular bag damage (crystalline or IOL)
- Microstent malposition
- Significant iris injury or trauma
- Vitreous loss
- Zonular dialysis

Postoperative adverse events include

- Angle closure
- Angle recession
- Anterior chamber cell or flare requiring either an increase in the standard postoperative steroid regimen or re-initiation of steroid use following completion of the standard postoperative steroid regimen.
- Aqueous misdirection
- Atrophy, phthisis
- Best-corrected visual acuity loss of 2 lines (10 letters) or more compared to baseline on the ETDRS chart measured before or at 1-month postoperative
- Best-corrected visual acuity loss of 2 lines (10 letters) or more compared to baseline on the ETDRS chart measured after 1-month postoperative
- Blebitis
- Choroidal detachment
- Choroidal hemorrhage or effusion (detachment with at least a partially hemorrhagic component that obstructs or causes pain, including both peripheral and "kissing" choroidal detachments) lasting 30 days or less
- Choroidal hemorrhage or effusion (detachment with at least a partially hemorrhagic component that obstructs or causes pain, including both peripheral and "kissing" choroidal detachments) lasting longer than 30 days
- Chronic anterior uveitis defined as inflammation of grade 1+ or worse persisting for more than 90 days postoperatively or that recurs less than 90 days after discontinuing standard medication regimen
- Chronic pain in the study eye onset ³ 3-months postoperative
- Corneal decompensation

- Corneal edema persisting > 30 days (mild to moderate) or severe corneal edema ≥ 1 day.
- Corneal opacification
- Descemet's membrane detachment
- Device migration (dislodgement or movement)
- Device obstruction
- Elevated mean IOP ≥ 10 mmHg than the qualifying baseline mean IOP onset before or at 1-month postoperative
- Elevated mean IOP ≥ 10 mmHg than the qualifying baseline mean IOP onset after 1-month postoperative
- Endophthalmitis

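### The primary analysis has no rule for study-eye surgery during follow-up, so an eye that has unforeseen cataract surgery is scored on its post-surgery IOP and can count as a Hydrus responder

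*Combined protocol and SAP*

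**What the plan says.** Section 5.3.1 defines a responder by a fall of at least 20%, that is, a "decrease in mean diurnal IOP at 12 months while maintaining the same or fewer number of medications as at baseline". It adds that "The primary analyses of the primary endpoint will be based on the Effectiveness Population". Section 5.3.2 takes the mean change in diurnal IOP at 12 months. Neither section mentions surgery after implantation.

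Section 5.2 builds the Effectiveness Population from subjects who have the implantation surgery and "are not discontinued early from the study due to unrelated reasons such as death or relocation". It has no surgery rule. The Per Protocol list in the same section has three relevant items: "Subject meets all protocol eligibility criteria"; "Subject received secondary surgical intervention (SSI) for controlling IOP will be included and treated as non-responder"; and "Subjects without adverse events that lower IOP such as cyclodialysis cleft". It also allows further criteria to be set before data review and database closure.

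On the lens, section 3.3 excludes aphakia, anterior chamber lenses and "A need for additional ocular surgery (e.g., cataract surgery) or retinal laser procedure within the 12-month postoperative period". Phakic eyes remain eligible, and the schedule in section 4.0 grades lens opacity in phakic subjects at Screening and at 1, 6 and 12 months. Section 6.8.1 anticipates intraoperative lens damage ("Lens / capsular bag damage (crystalline or IOL") and, postoperatively, worsening lens opacity and surgical re-intervention in the study eye.

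**The concern.** The Screening exclusion can remove only a need that is foreseeable at Screening. It cannot remove a lens damaged during implantation, or an opacity that progresses faster than expected. If such an eye has its lens removed before month 12, the stated endpoint uses the IOP measured afterwards.

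If lens removal lowers IOP, part of the measured fall belongs to the second operation and not to the device. The plan describes no control arm and reports a single response rate with an exact interval, so the effect cannot cancel between groups. In the extreme case, an eye harmed by the implantation procedure and then operated on is recorded as a device success. The secondary mean change has the same gap. If the handling is settled only once results are visible, the choice may also be influenced by them.

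**Working it through.** **Step 1. Set the population rules in 5.2 side by side.**

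| Event | Effectiveness Population (primary) | Per Protocol |
|---|---|---|
| Early exit for unrelated reasons | removed | removed (12-month visit required) |
| Surgery to control IOP | no rule | non-responder |
| Adverse event that lowers IOP | no rule | removed |
| Cataract or other study-eye surgery | no rule | no explicit rule |

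The gap in the primary analysis is therefore general: even surgery done to control IOP is not defined there as non-response. Cataract surgery is the instance that the eligibility criteria and the anticipated events make plausible.

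**Step 2. Fall needed for response.** Eligible medicated IOP is 20 to 35 mmHg (3.2, 3.4). The threshold is 0.20 x baseline: 0.20 x 20 = 4.0 mmHg and 0.20 x 35 = 7.0 mmHg.

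**Step 3. Share of that threshold that lens removal could supply.** The documents give no effect size, so 1 to 4 mmHg is assumed. Share = effect / threshold.
- Baseline 20: 1/4 = 25%; 2/4 = 50%; 4/4 = 100%.
- Baseline 35: 1/7 = 14%; 2/7 = 29%; 4/7 = 57%.

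Lens removal need not make an eye a responder, but it can tip an eye that is near the threshold.

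**Step 4. Ceiling on the response-rate bias.** The documents give neither the phakic share nor the surgery rate. Assume 30-60% phakic and 3-10% of those operated on within 12 months.
- Low: 0.30 x 0.03 = 0.9% of subjects.
- High: 0.60 x 0.10 = 6% of subjects.

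The bias cannot exceed these shares. It reaches them only if every operated eye responded solely because of lens removal.

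**Step 5. Effect of recoding on the reported result.** The supplied text gives no sample size or target rate, so there is no figure of the plan's own to reproduce. As an illustration, assume N = 50 with 30 responders and recode k operated responders as non-responders (exact 95% intervals).
- k = 0: 30/50 = 60.0% (45.2 to 73.6).
- k = 1: 29/50 = 58.0% (43.2 to 71.8).
- k = 3, which is 6% of 50: 27/50 = 54.0% (39.3 to 68.2).

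Each recoded eye moves the rate by 1/50 = 2 points.

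**Step 6. Secondary endpoint.** Shift in mean change = share operated on x effect: 0.009 x 1 = 0.009 mmHg to 0.06 x 4 = 0.24 mmHg.

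**The case against.** The strongest case on the other side has four parts.

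First, section 3.3 already screens out foreseeable cataract surgery, so few eyes may be left. This stands and limits the frequency. It does not define the endpoint for the eyes that remain.

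Second, the Per Protocol analysis may already reach these eyes. Re-intervention is an anticipated adverse event, IOP-lowering adverse events are removed, the eligibility criterion might be read in retrospect, and further criteria may be added. This is open to interpretation and in any case applies only to Per Protocol. It does show that the sponsor does not want IOP falls from other causes credited in that analysis.

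Third, no passage says that lens removal lowers IOP, and the plan's silence is not a stated instruction to use the post-surgery value. Both points are fair. The favourable direction is an assumption, and using the observed value is the literal reading of a definition that makes no exception. The endpoint needs a rule whatever the effect size.

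Fourth, the supplied text gives no performance goal that a shift of this size could overturn. That also stands, and it keeps the point moderate.

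A reader might infer that the fall is credited because cataract surgery is not done to control IOP. The documents do not support that reason for the primary analysis: the phrase belongs to the Per Protocol list, and rewording it would leave the Effectiveness Population unchanged. A reader might also infer from section 3.3 that the sponsor judged cataract surgery incompatible with reading the 12-month result. The section gives no rationale and groups it with other ocular surgery and retinal laser.

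**Conclusion.** The point holds as a gap in the definition of both effectiveness endpoints. In the Effectiveness Population, an eye that has unforeseen cataract surgery is scored on its post-surgery IOP. It counts as a Hydrus responder if it shows the 20% fall on no more medications than at baseline.

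The response-rate bias is at most the share of eyes operated on. That share is 0.9% to 6% under the assumed phakic share and surgery rate, and the bias is probably smaller, because some operated eyes would have responded anyway and others will not respond. The shift in mean change is about 0.01 to 0.24 mmHg if the effect is 1 to 4 mmHg. Both shifts favour the device if lens removal lowers IOP. It would go too far to say that every operated eye becomes a success, or to read 1-6 points as an estimate; the documents support only a ceiling that depends on assumptions.

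The change should be made: the number of eyes is probably small, but the literal rule gives the favourable answer and the remedy is cheap.

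**What to change.** **5.3.1.** State that, in the Effectiveness Population, an eye having lens surgery, or other study-eye surgery that can alter IOP, before the 12-month diurnal IOP is a non-responder. Add a sensitivity analysis that scores such eyes on their observed 12-month value.

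**5.3.2.** Do not use IOP measured after such surgery. Treat the 12-month diurnal value as missing under a stated imputation, for example zero change from baseline, with the observed value as a sensitivity analysis. Do not carry forward the last reading before surgery: as the schedule in section 4.0 reads, intermediate visits collect ordinary IOP, so a non-diurnal and possibly early value would enter a diurnal endpoint.

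**Data capture.** Record study-eye surgery explicitly on the case report form, with its date and reason, and report the number of such eyes. Adverse event recording alone does not assure this. Section 6.7 records surgery only as an action taken for an event, section 6.1 tells sites not to record natural progression of a chronic condition, and section 6.2 says that treatment is not itself the event.

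These rules should be fixed before database closure. The cost is a few sentences, one form item, a little more analysis and a slightly lower response rate. The non-responder rule is conservative for an eye that was already responding before its lens surgery; the sensitivity analysis shows how much that matters.
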